Statistical Analysis Plan (SAP)

Study Title:	OBdIPHY (OBesity DIgital-PHYsical care study) Effects of digital-physical care for families with children and adolescents living with obesity
Study Registration Number:	276515 (Clinicaltrials.gov)
Sponsor:	Research council, Region Halland, Sweden The Sparbanken Foundation, Varberg, Sweden VINNOVA Winter project, Sweden Southern healthcare region project support, Sweden The Jerring foundation, Sweden Grants from the Swedish state under the agreement between the Swedish government and the county councils, the ALF-agreement (ALFGBG-984419)
Intervention:	Semi-digital care for childhood obesity with digital treatment meetings and an app as support for lifestyle treatment.
Protocol Number:	ClinicalTrials no 276515
Statistical Analysis Plan Version:	Version 1.0
Statistical Analysis Plan Date:	2025-04-17
Author:	[name], Region Halland, [name]

SAP Primary Author: [name]

Senior Statistician: [name]

SAP Contributor (Primary Investigation): [name]

SAP Contributor (Co-supervisor): [name]

Abbreviations

BMiz Body Mass Index z-score

OBDIPHY Obesity digital-physical care study

SAP Statistical Analysis Plan

1. Introduction

The aim of this project is to study the safety and effectiveness of semi-digital lifestyle treatment for childhood obesity. This statistical analysis plan (SAP) defines the statistical methods that will be used for the final analyses of the data collected in the trial OBDIPHY (Obesity digital-physical care study). The SAP was created based on the project plan registered at ClinicalTrial.gov, id no 276515 registered 12/07/2021.

2. Overview and objectives for study design

This is a prospective randomized controlled multicentre non-inferiority trial, conducted in three different councils in southwest of Sweden. The aim of this study was to evaluate semi-digital care compared to regular physical/in person care and evaluate if semi-digital care is non-inferior to standard care among families with children or adolescents aged 10-16 year living with obesity in Sweden. The study participants either received treatment as usual or treatment as usual combined with a semi-digital solution. The semi-digital solution includes that half of the sessions are digital and an app where the participants could self-monitor health data, have an overview over they treatment plan and easy communication with their caregivers.

The null hypothesis is that semi-digital care will have an effect and decrease body mass index z-score (BMI_z), however inferior to treatment as usual. In addition to evaluating the new treatment alternative, BMI_z, weight development and metabolic risk factors and food habits during the study will also be evaluated. See figure 1 for study design.

[figure not shown]

Figure 1. Study design.

The inclusion of participants started in March 2022 and was planned to end in December 2022, but was extended to the end of May 2023. The last participants had their one-year visit in May 2024. Unfortunately, due to organisational and structural challenges the Skåne site had difficulties to provide both the digital and the standard care. Participants from the Skåne site therefore did not receive care in accordance with the study protocol. Due to severe protocol violation, the participants from the Skåne site were excluded as per decision by the study steering committee on the 5th of December 2024, prior to any data analyses.

3. Outcomes and analyses

Descriptive data will be presented using mean and standard deviation (SD) if the data is normally distributed, otherwise median and interquartile range (IQR) will be presented. Binary and categorical variables will be presented using number and percentage.

3.1 Primary outcome

The primary outcome of this clinical trial is the change in BMI_z from baseline to 12 months. The hypothesis of the study is that the change in BMI_z in the intervention group is non-inferior to the control group. This will be analysed using a non-inferiority approach.

3.2 Secondary outcomes

The effect of semi-digital care on change in BMI_z, weight, metabolic markers and dietary habits after one year (for BMI_z and weight also at 3, 6 and 9 months) will be investigated.

Analyses: For continuous variables regarding change in BMI_z, weight and blood markers the means between the groups will be compared. A non-parametric test to compare frequencies for categorical variables will be used. We will also use logistic regression models to evaluate the odds for change in zBMI larger than 0.25 sd.

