3.3 Exploratory analyses

Exploratory analyses guided by the findings will be performed.

4. Population

A power calculation was performed, based on a change of 0.21 BMI_z at 12 months with a standard deviation of 0.24 in the standard care group, and with a non-inferiority limit of 0.12 BMI_z between the groups. To reach 80 % power with a significant level of 0.05, a study population of 100 participants, 50 in each group was needed.

5. Missing data

In the case of missing data, the last observation carried forward approach will be used when data is available from 6- or 9-month follow up. Values that are outside the time-range for the visits will be included in the analysis when needed.

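### No covariates are prespecified for the continuous outcomes, including the primary, so the plan gives up a modest amount of precision that data already collected could supply

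*SAP*

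**What the plan says.** Section 3.1 defines the endpoint: "The primary outcome of this clinical trial is the change in BMI_z from baseline to 12 months". Its method is given in one sentence: "This will be analysed using a non-inferiority approach". That sentence names no estimator, model, covariate or confidence level.

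Section 3.2 is the only place that says how a continuous outcome is compared between arms: "For continuous variables regarding change in BMI_z, weight and blood markers the means between the groups will be compared". No covariate is listed. The logistic model in the same section, for a BMI_z change larger than 0.25, lists none either.

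Section 4 gives the design inputs: "based on a change of 0.21 BMI_z at 12 months with a standard deviation of 0.24 in the standard care group", "with a non-inferiority limit of 0.12 BMI_z between the groups", and a requirement stated as "a study population of 100 participants, 50 in each group was needed".

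Section 2 describes a randomised trial in three councils, enrolling ages 10 to 16, with the Skåne participants later excluded.

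**The concern.** A change score uses the baseline value with a fixed coefficient of one. Unless baseline and follow-up are almost perfectly correlated, that is not the most precise use of it. Change then remains negatively related to baseline, and this leftover relation adds noise to the comparison. It also means that, in a given randomisation, an arm that happens to start higher will tend to show a larger fall. Regression on the baseline value removes both effects and, in large samples, cannot increase the variance of the treatment estimate.

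This matters because the design has little slack: non-inferiority is claimed only if the confidence interval excludes 0.12, and the planned size delivers almost exactly 80% power. Site is a plausible source of variation in a multicentre trial of care delivery. For raw weight, growth between 10 and 16 differs greatly by age and sex. If no covariates are fixed in advance, any adjustment chosen later could be seen as guided by the data.

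**Working it through.** **Inputs from Section 4.** Margin 0.12; SD of change 0.24; 50 per arm; 80% power; significance level 0.05, sidedness not stated. The true difference between arms is taken as 0 (assumption).

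**Step 1: reproduce the sample size.** n per arm = 2 × [SD × (z₁₋α + z₀.₈₀) / margin]².

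- One-sided 0.05: 2 × [0.24 × (1.645 + 0.842) / 0.12]² = 49.46, rounded up to 50. This matches the SAP.
- One-sided 0.025: 62.79, rounded up to 63. This does not match.

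The stated size therefore corresponds to one-sided 0.05 and the full SD of change, with no credit for covariates.

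**Step 2: power at 50 per arm without covariates.** SE = 0.24 × √(2/50) = 0.048, and 0.12 / 0.048 = 2.5. Power = Φ(2.5 − 1.645) = 80.4% at one-sided 0.05, and Φ(2.5 − 1.96) = 70.5% at one-sided 0.025. The 90% CI half-width is 1.645 × 0.048 = 0.079.

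**Step 3: power with covariates.** Let R² be the share of the variance of change that the covariates explain, and replace the SD by 0.24 × √(1 − R²). The SAP gives no R², so a range is assumed.

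| R² (assumed) | SD | Power, one-sided 0.05 | Power, one-sided 0.025 | n per arm for 80% (one-sided 0.05) | 90% CI half-width |
|---|---|---|---|---|---|
| 0 | 0.240 | 80.4% | 70.5% | 50 | 0.079 |
| 0.05 | 0.234 | 82.1% | 72.7% | 47 | 0.077 |
| 0.10 | 0.228 | 83.9% | 75.0% | 45 | 0.075 |
| 0.20 | 0.215 | 87.5% | 79.8% | 40 | 0.071 |

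The equivalent gain in sample size is 1/(1 − R²): about 5%, 11% and 25%.

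**Step 4: which R² is plausible from baseline alone.** With equal SDs at both visits and correlation ρ, the variance of change is 2σ²(1 − ρ) and the ANCOVA residual variance is σ²(1 − ρ²). Their ratio is (1 + ρ)/2. So ρ = 0.9 gives R² = 0.05, ρ = 0.8 gives 0.10, and ρ must be as low as 0.6 to give 0.20. The SAP does not give ρ. If it lies between 0.8 and 0.9, the gain is about 2 to 4 power points.

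**Step 5: effect of a chance imbalance.** Under the same assumptions the SD implied at each visit is σ = 0.24 / √[2(1 − ρ)]: 0.379 at ρ = 0.8 and 0.537 at ρ = 0.9. A baseline difference of one standard error, σ × √(2/50), shifts the difference in mean change by (1 − ρ) times that amount:

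- ρ = 0.8: 0.2 × 0.379 × 0.2 = 0.015, or 13% of the margin.
- ρ = 0.9: 0.1 × 0.537 × 0.2 = 0.011, or 9% of the margin.

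**Step 6: the cost if covariates are useless.** With four covariates and R² = 0, the residual degrees of freedom fall from 98 to 94 and the variance is inflated by about 1 + 4/93 = 1.043. Power based on the t distribution falls from 79.9% to 78.4%.

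**The case against.** The strongest reply is that nothing here is an error. A difference in mean change is a valid analysis and agrees with the SAP's own sample size. That stands: the point concerns efficiency and prespecification.

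Several stronger readings are tempting but not supported.

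- **That the SAP prescribes an unadjusted analysis.** It does not use that word, and adjusted means are also compared means. What can be said is that no covariate is named. For the primary outcome the reading is weaker still, because the sentence on comparing means stands under secondary outcomes and Section 3.1 gives no estimator at all.
- **That the comparison is biased.** Randomisation makes it unbiased on average. Only the estimate from a particular randomisation that happens to be imbalanced is shifted, as in Step 5.
- **That excluding the Skåne site makes harmful imbalance more likely.** The SAP does not say whether randomisation was stratified by site or how many participants remain. If it was stratified, removing a whole site leaves the balance within the others intact.
- **That age and sex would sharpen the primary analysis.** A BMI z-score is normally already standardised for both, so little should be expected. The argument applies to weight and blood markers, for which the SAP gives no figures from which to compute a gain.
- **That adjustment costs nothing.** Step 6 shows a small cost if the covariates are uninformative.

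**Conclusion.** The point holds as a modest improvement. The SAP names no covariate for any continuous comparison and so leaves unused the precision that the baseline value and site could provide. The planned comparison remains valid and unbiased over randomisation.

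At 50 per arm and one-sided 0.05, power would rise from 80.4% to about 82–84% if covariates explain 5–10% of the variance of change, and to 87.5% if they explain 20%. The first range is the more likely for BMI_z, because the change score already uses the baseline. These figures rest on the SAP's SD of 0.24, a true difference of 0, an assumed R², and the planned rather than the remaining sample size. The possible loss is about 1.5 power points.

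**What to change.** Prespecify ANCOVA for the primary and the continuous secondary outcomes. Regress the 12-month value on arm, the baseline value of the same variable, and site. Using change as the response gives the same arm effect once baseline is in the model. Add age and sex for weight and blood markers.

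State in Section 3.1 that non-inferiority is judged by comparing the confidence interval of the adjusted difference with 0.12, and give its level. Keep the unadjusted difference in mean change as a supporting result.

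The cost is a paragraph in Sections 3.1 and 3.2 and a few degrees of freedom. No new data are needed. The covariate list should be fixed before outcomes are compared by arm. If that comparison has already been made, the adjusted analysis should be reported as added afterwards.

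### Dietary habits: the objective is change, but the planned comparison of frequencies includes no baseline answer and is inefficient for ordered items

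*SAP*

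**What the plan says.** SAP section 3.2 gives the secondary target as the effect of semi-digital care on "change in BMI_z, weight, metabolic markers and dietary habits after one year". It then assigns methods in three sentences:

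- "For continuous variables regarding change in BMI_z, weight and blood markers the means between the groups will be compared". Dietary habits are not in this list.
- "A non-parametric test to compare frequencies for categorical variables will be used". No test is named and no outcome is listed.
- "We will also use logistic regression models to evaluate the odds for change in zBMI larger than 0.25 sd". This is the only regression model in the plan. It concerns BMI_z, and no covariates are given.

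Dietary habits are the one listed outcome left over, so by elimination they belong to the second sentence. The SAP does not say so directly and does not describe the dietary items. Section 3 promises counts and percentages as descriptive statistics for binary and categorical variables. No confidence interval for a dietary effect is planned anywhere.

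**The concern.** For the continuous outcomes the plan says that change is what is compared. For diet it states a change objective and then gives a method that mentions neither change nor baseline. The mismatch lies within one section, so it is not detail left to an unseen protocol.

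The natural reading of the frequency sentence is a chi-square or Fisher test on the 12-month answers. Such a test sets aside what each child answered at baseline and treats ordered categories as if they were unordered. With about 50 children per arm, both losses can matter. The output would be a p-value beside two sets of percentages. In a trial framed around non-inferiority, a non-significant p-value without an interval invites being read as showing that diet is the same under both care models.

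**Working it through.** **The plan's own figure.** The SAP gives no figure for diet. Its only sample-size statement (section 4) is for BMI_z: "To reach 80 % power with a significant level of 0.05, a study population of 100 participants, 50 in each group was needed". The inputs it uses are an SD of 0.24 and a margin of 0.12. With no true difference, n per arm = 2 × (z for alpha + z for power)² × (SD/margin)².

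- One-sided alpha 0.05: 2 × (1.645 + 0.842)² × (0.24/0.12)² = 49.5, so 50 per arm and 100 in total. This reproduces the plan.
- One-sided alpha 0.025: 2 × (1.960 + 0.842)² × 4 = 62.8, so 63 per arm and 126 in total. This does not.

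The calculation does not bear on diet. It supplies only the 50 per arm used below.

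**Assumptions not in the SAP.** A normal latent answer is cut into K equal-probability categories. The latent correlation between baseline and 12 months is 0.3, 0.5 or 0.7. The true shift is 0.5 latent SD. Tests are two-sided at 0.05, with 600 simulated trials per cell. The Monte Carlo standard error near 50% is √(0.5 × 0.5/600) = 0.020, about 2 points.

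**Power (%) at 50 per arm**

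| K | Correlation | Chi-square, 12-month answers | Mann-Whitney, 12-month answers | Chi-square, worse/same/better | Logistic or proportional odds with baseline |
|---|---|---|---|---|---|
| 2 | 0.3 | 51.3 | 51.3 | 25.2 | 52.7 |
| 2 | 0.5 | 51.7 | 51.7 | 28.3 | 57.2 |
| 2 | 0.7 | 47.7 | 47.7 | 33.8 | 57.7 |
| 3 | 0.3 | 47.8 | 59.3 | 30.8 | 62.2 |
| 3 | 0.5 | 51.2 | 62.2 | 40.7 | 67.2 |
| 3 | 0.7 | 47.8 | 58.2 | 51.2 | 74.8 |
| 5 | 0.3 | 40.5 | 62.8 | 34.0 | 67.7 |
| 5 | 0.5 | 40.7 | 63.2 | 44.0 | 73.8 |
| 5 | 0.7 | 40.7 | 61.0 | 58.8 | 84.3 |

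**Four ordered categories.** One run gave chi-square 47/45/42% across the three correlations, the ordinal model without baseline 64/63/60%, and with baseline 66/73/81%. A separate run gave chi-square 41/44/48% and the adjusted model 63/72/81%.

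**Yes/no items again.** A separate run gave chi-square 55/50/56% and the adjusted model 52/56/61%, differences of −3, +6 and +5 points. Together with the table (+1.4, +5.5, +10.0), the binary gain ranges from about none to 10 points.

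**Source of the gain.** Mann-Whitney on 12-month answers uses order but not baseline, so it separates the two.

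- K = 5, correlation 0.3: total gain 67.7 − 40.5 = 27.2 points, of which order gives 62.8 − 40.5 = 22.3.
- K = 5, correlation 0.7: total gain 84.3 − 40.7 = 43.6 points, of which order gives 61.0 − 40.7 = 20.3.

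At low correlation, most of the gain therefore comes from order.

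**Type I error.** At 50 per arm it ran from 4.0% to 7.2% over all methods and cells. The highest value was for the adjusted model (K = 5, correlation 0.3), so its power there may be slightly flattered.

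**Smaller sample.** Section 2 excludes one site without giving a number. At an illustrative 35 per arm with K = 5, chi-square had 31/29/27% and the adjusted model 52/58/70%. With K = 2 the figures were 33/35/36% and 37/40/48%.

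**The case against.** The strongest reply is that the plan leaves the test unnamed, so it cannot be faulted for a particular one. Three points of it stand.

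- **Baseline and order.** A reader might infer that the plan discards both. The document does not say that. Frequencies of worse, same and better would use the baseline answer, and a rank or trend test is non-parametric and uses order. What can be said is that neither is mentioned. The change-category reading does not rescue efficiency: chi-square on worse/same/better reached only 25–59% in the table.
- **Item format.** A dietary score would not fall under the frequency sentence at all, and the instrument may be described in the protocol. A large power gain therefore cannot be claimed for dietary outcomes in general, and for yes/no items it is small.
- **Validity.** Comparing 12-month frequencies between randomised arms is a legitimate test, and its type I error was close to nominal.

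A reader might also infer that a null dietary result would mostly reflect the choice of test. The figures do not support this in general. With four categories and correlation 0.3, chi-square misses 100 − 47 = 53% of true effects and the adjusted model still misses 100 − 66 = 34%, so 34/53, or 64%, of the misses remain. At correlation 0.5 it is 27/55, or 49%. Only at 0.7, with 19/58 or 33%, does the test account for most of them. A sample size set for BMI_z is the larger limit when correlation is low.

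The objection does not remove the gap between a change objective and a method sentence with no baseline term, or the lack of an interval estimate.

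**Conclusion.** The point holds as a matter of efficiency and clarity for one secondary outcome. SAP section 3.2 targets change in dietary habits. The only method that appears to apply names no test, includes no baseline answer, is silent on category order, and yields no effect estimate with a confidence interval.

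On the natural reading, power is about 40–50%, against about 62–84% for a baseline-adjusted proportional-odds model with three to five ordered categories. For binary items at 50 per arm the difference is about none to 10 points. These figures rest on an assumed item format, a 0.5 SD latent shift and correlations of 0.3 to 0.7, none of which the SAP gives. The size is a range under assumptions, and the documents do not show that the planned test is wrong.

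**What to change.** State the dietary items and their scale, and replace the frequency sentence in section 3.2 with:

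*Categorical outcomes at 12 months will be analysed by logistic regression (binary) or proportional-odds logistic regression (ordered categories) with arm and the baseline category as covariates, reported as odds ratio with 95% CI; unordered items will be compared by chi-square or Fisher exact test.*

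The last clause still leaves out the baseline answer for unordered items, a limit accepted for simplicity.

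The cost is a short change of wording and slightly more analysis. A change objective already presupposes baseline answers, so no new data are needed. The main downside is the proportional-odds assumption for ordered items. If dietary results have already been examined by arm, the change should be dated and labelled as made after that.

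### Carry-forward from month 6 or 9 also decides who counts as passing the 0.25 cut, so the responder odds ratio can shift with drop-out, in either direction

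*SAP*

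**What the plan says.** Section 3.2 (Secondary outcomes) compares group means for continuous changes and then adds: "We will also use logistic regression models to evaluate the odds for change in zBMI larger than 0.25 sd". The sentence gives neither a time point nor a direction. The secondary outcomes are set at one year, and "for BMI_z and weight also at 3, 6 and 9 months".

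Section 5 (Missing data) has one imputation rule for the whole plan: "the last observation carried forward approach will be used when data is available from 6- or 9-month follow up". It continues: "Values that are outside the time-range for the visits will be included in the analysis when needed". Neither section exempts the responder analysis, gives it a separate rule, or names a sensitivity analysis. Nothing is said about children with neither a 6- nor a 9-month value.

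The only figures for expected change are in Section 4 (Population). The sample size is "based on a change of 0.21 BMI_z at 12 months with a standard deviation of 0.24 in the standard care group", "with a non-inferiority limit of 0.12 BMI_z between the groups". The SAP gives no expected change, standard deviation or responder rate at month 6 or 9, and no expected drop-out rate.

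**The concern.** Read together, Sections 3.2 and 5 give a child without a 12-month value a responder status taken from month 6 or 9. The logistic model then treats that status as a 12-month observation. Two problems follow.

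- **Mixed time points.** The proportion above the cut in each arm becomes a blend of the 12-month proportion and an earlier one, weighted by the share carried forward. If the two differ, unequal carried shares can move the odds ratio away from 1 when the arms are equal, and can shrink or exaggerate a real difference.
- **Overstated precision.** The standard error takes an imputed status as known.

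A cut is sensitive to this. The expected 12-month mean of 0.21 lies only 0.04 below 0.25, which is 0.04/0.24 = 0.17 SD, so many children sit close to the line. In a non-inferiority trial, a supporting analysis that can understate a deficit deserves a deliberate rule.

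**Working it through.** **Inputs from the SAP.** Section 4: mean change 0.21 and SD 0.24 at 12 months in standard care, limit 0.12, 50 per group. Section 3.2: cut 0.25.

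**The plan's own figure.** With no true difference, 80% power and one-sided 0.05, n per group = 2 × 0.24² × (1.645 + 0.842)² / 0.12² = 49.5, so 50 per group and 100 in total, as stated. (One-sided 0.025 would need 63 per group. The SAP does not state the sidedness.) This confirms that 0.24 and 0.12 are the working inputs. The 0.21 does not enter the formula.

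**Assumptions, not in the SAP.** Response is a decrease above 0.25 BMI_z units at 12 months. Changes are normal. Children who drop out follow the same course as the others in their arm. The SD is either 0.24 throughout or 0.24 × √(t/12). Trajectory and carried shares are varied.

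**Step 1. Proportion above the cut**, P = Φ((mean decrease − 0.25)/SD).

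- Month 12: Φ(−0.04/0.24) = 43.4%.
- Month 6, linear (mean 0.105): Φ(−0.145/0.24) = 27.3% with constant SD; Φ(−0.145/0.170) = 19.6% with growing SD.
- Month 9, linear (mean 0.1575): 35.0% and 32.8%.

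**Step 2. Equal arms.** Arm proportion = (1 − q) × P12 + q × P(carried), where q is the share carried. Example with growing SD, all carried from month 6:

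- standard care, q = 0.30: 0.7 × 0.434 + 0.3 × 0.196 = 0.363
- semi-digital, q = 0.10: 0.9 × 0.434 + 0.1 × 0.196 = 0.410
- odds ratio = (0.410/0.590)/(0.363/0.637) = 1.22

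Odds ratios, semi-digital against standard care, when the true value is 1 (ranges cover the two SD assumptions):

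| Trajectory | Carried from | 10% semi-digital, 30% standard | 30% semi-digital, 10% standard |
|---|---|---|---|
| Linear | month 6 | 1.14-1.22 | 0.82-0.88 |
| Linear | half from each | 1.11-1.15 | 0.87-0.90 |
| Linear | month 9 | 1.07-1.09 | 0.92-0.93 |
| Three quarters of the change by month 6 | month 6 | 1.07-1.12 | 0.89-0.93 |
| Plateau by month 6 | month 6 | 1.00-1.02 | 0.98-1.00 |
| Larger early change (1.25 times at month 6), then rebound | month 6 | 0.93 | 1.07-1.08 |

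With 20% carried in both arms the odds ratio is 1.00 in every row.

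**Step 3. True difference at the limit.** Semi-digital mean 0.21 − 0.12 = 0.09, so P12 = Φ(−0.16/0.24) = 25.2%. The true odds ratio is (0.252/0.748)/(0.434/0.566) = 0.44. With linear change in both arms and values carried from month 6:

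- 10% semi-digital, 30% standard: 0.52-0.55
- 20% in both: 0.46-0.47
- 30% semi-digital, 10% standard: 0.38-0.43

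**The case against.** **Trajectory.** A reader might infer that far fewer children have passed the cut at month 6 or 9, because change builds up over the year. The SAP does not say so. Its one figure is for month 12. The gap is about 16 to 24 points at month 6 and 8 to 11 at month 9 if change is linear, but it disappears with a plateau and reverses with rebound.

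**Direction.** A reader might also infer that carry-forward favours semi-digital care. That needs more drop-out in standard care, and the SAP gives no rate or direction. Swapping the shares exaggerates the deficit instead. With equal arms, equal trajectories and equal drop-out there is no shift.

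**Amount carried.** Only children without a 12-month value are affected. The latest value is used, so month 9 displaces month 6 where both exist, and admitting out-of-window visits may reduce the share carried. All three tend to bring the result nearer the milder rows.

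**Size against precision.** At the planned 50 per arm and 43.4% response, the standard error of the log odds ratio is √(2/(50 × 0.434 × 0.566)) = 0.40, so a 95% interval around 1 runs from about 0.45 to 2.2. An odds ratio of 1.22 is a shift of half a standard error; 1.07-1.09 is about a fifth.

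**Role.** The time point and direction are inferred, and the primary comparison in Section 3.1 does not rest on this model.

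These points stand, and they limit the claim to a conditional one. They do not make the rule sound. Carry-forward is harmless here only under particular patterns of change or drop-out, and the SAP argues for none of them. The uncertainty of the imputed status is ignored whatever the trajectory.

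**Conclusion.** The point holds in conditional form. The carry-forward rule in Section 5 covers the 0.25 analysis in Section 3.2, so a child missing at 12 months is classed from month 6 or 9 and treated as observed. If change differs between those visits and month 12, the odds ratio blends time points and depends on how much drop-out there is and how it is balanced.

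Under the linear illustration with shares of 30% and 10%, a true odds ratio of 1 is estimated at anything from 0.82 to 1.22, and a true 0.44 at roughly 0.38 to 0.55. These are illustrations of what could happen. They depend on an assumed trajectory and assumed drop-out, and the document fixes neither the size nor the sign. The consequence is confined to a secondary analysis, so the change is advisable rather than critical.

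**What to change.** In Section 3.2, state that response is a decrease in BMI_z above 0.25 from baseline to 12 months, if that is what is meant. In Sections 3.2 and 5, take this analysis out of the carry-forward rule:

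1. Multiply impute the continuous 12-month BMI_z within each arm from baseline and the observed 3-, 6- and 9-month values.
2. Apply the 0.25 cut in each completed data set.
3. Fit the logistic model in each and combine by Rubin's rules.
4. Report the carry-forward result as a sensitivity analysis only, with the number of carried values by arm and by source visit.

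This also covers children with neither a 6- nor a 9-month value, whom the present rule leaves unaddressed. The cost is a change of wording and one routine imputation run, with no new data, since Section 3.2 already plans to analyse BMI_z at these visits. The downside is reliance on a missing-at-random assumption and a somewhat wider confidence interval, which reflects the uncertainty that carry-forward hides.
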